8.3.4. Regulatory Reporting Requirements for Serious Adverse Events

The sponsor assumes responsibility for appropriate reporting of AEs to the regulatory authorities. The sponsor will also report to the investigator (and the head of the investigational institute where required) all suspected unexpected serious adverse reactions (SUSARs). The investigator (or sponsor where required) must report SUSARs to the appropriate Independent Ethics Committee/Institutional Review Board (IEC/IRB) that approved the protocol unless otherwise required and documented by the IEC/IRB. A SUSAR will be reported to regulatory authorities

unblinded. Participating investigators and IEC/IRB will receive a blinded SUSAR summary, unless otherwise specified.

8.3.5. Pregnancy

All initial reports of pregnancy in participants or partners of male participants must be reported to the sponsor by the study-site personnel within 24 hours of their knowledge of the event using the appropriate pregnancy notification form. Abnormal pregnancy outcomes (eg, spontaneous abortion, fetal death, stillbirth, congenital anomalies, ectopic pregnancy) are considered SAEs and must be reported using an SAE reporting form. Any participant who becomes pregnant during the study must discontinue further study vaccination but will remain in the study and will continue to undergo all procedures for follow-up and all safety follow-up as outlined in the protocol for all participants.

Follow-up information regarding the outcome of the pregnancy and any postnatal sequelae in the infant will be required.

8.3.6. Adverse Events of Special Interest

Adverse events of special interest (AESIs) are significant AEs that are judged to be of special interest because of clinical importance, known or suspected class effects, or based on nonclinical signals. Adverse events of special interest will be carefully monitored during the study by the sponsor.

AESIs must be reported to the sponsor within 24 hours of awareness irrespective of seriousness (ie, serious and non-serious AEs) or causality following the procedure described above for SAEs.

Specific requirements for the AESI are described below.

8.3.6.1. Thrombosis with Thrombocytopenia Syndrome

As described in Section 2.3.1, Risks Related to Study Participation, TTS has been observed very rarely following vaccination with Ad26.COV2.S and is considered to be an AESI in this study. TTS is a syndrome characterized by a combination of both a thrombotic event and thrombocytopenia (American Society of Hematology 2021, Brighton Collaboration. Interim Case Definition of Thrombosis with Thrombocytopenia Syndrome 2021).

Because this syndrome is rare and not completely understood, all cases of thrombosis and/or thrombocytopenia will be considered a suspected case of TTS until further adjudication can be performed. An AESI Adjudication Committee with appropriate expertise will be established to evaluate each suspected AESI and determine whether it is a case of TTS. The investigator shall be responsible for reporting any suspected AESI of TTS using the SAE form and the form detailed in Section 10.8, Appendix 8. A suspected TTS case is defined as:

- Thrombotic events: suspected deep vessel venous or arterial thrombotic events as detailed in Section 10.9, Appendix 9

- Thrombocytopenia, defined as platelet count below 150,000/ μ L (Brighton Collaboration. Interim Case Definition of Thrombosis with Thrombocytopenia Syndrome 2021)

Symptoms, signs, or conditions suggestive of a thrombotic event should be recorded and reported as a suspected AESI even if the final or definitive diagnosis has not yet been determined, and alternative diagnoses have not yet been eliminated or shown to be less likely. Follow-up information and final diagnoses, if applicable, should be submitted to the sponsor as soon as they become available.

In the event of thrombocytopenia, study site personnel should report the absolute value for the platelet count and the reference range for the laboratory test used.

For either a thrombotic event or thrombocytopenia, testing for anti-PF4 may be performed at the local laboratory or substitute local laboratory; repeat testing may be requested for confirmation upon sponsor discretion.

Suspected AESIs will require enhanced data collection and evaluation (see Section 1.4.3). Every effort should be made to report as much information as possible about the AESI to the sponsor in a reasonable timeframe.

If an event meets the criteria for an SAE (Section 10.4.1), it should be reported using the same process as for other SAEs.

The form detailed in Section 10.8, Appendix 8 is intended as a guide for assessment of the AESIs to facilitate diagnosis and determine treatment options. If the investigator is not the treating physician, every effort should be made to collect the information requested in the form from the treating physician and enter the available information in the eCRF.

9. STATISTICAL CONSIDERATIONS

Statistical analysis will be done by the sponsor or under the authority of the sponsor. A general description of the statistical methods to be used to analyze the immunogenicity and safety data is outlined below. Specific details will be provided in the SAP.

9.1. Statistical Hypotheses

Formal NI testing will be applied to demonstrate NI of 1-dose and 2-doses of 9×10^{10} vp, 2.5×10^{10} vp, 7×10^{10} vp, 3.5×10^{10} vp, and 1.25×10^{10} vp Ad26.COV2.S versus 1- dose and 2-doses of 5×10^{10} vp Ad26.COV2.S (release titer), using a NI margin of 2/3 for the GMC ratios.

The 2.5×10^{10} vp dose will be tested before the 7×10^{10} vp in the sequential testing due to an increased risk to fail non-inferiority as a consequence of a smaller sample size in the 7×10^{10} vp group as shown in Table 7.

The following 2 sets of hypotheses (1 dose and 2 doses) will independently be tested sequentially:

Post-dose 1

- 1a) NI after 1-dose of Ad26.COV2.S 9×10^{10} vp versus 1-dose of Ad26.COV2.S 5×10^{10} vp (release titer)
- 1b) NI after 1-dose of Ad26.COV2.S 2.5×10^{10} vp versus 1-dose of Ad26.COV2.S 5×10^{10} vp (release titer)
- 1c) NI after 1-dose of Ad26.COV2.S 7×10^{10} vp versus 1-dose of Ad26.COV2.S 5×10^{10} vp (release titer)
- 1d) NI after 1-dose of Ad26.COV2.S 3.5×10^{10} vp versus 1-dose of Ad26.COV2.S 5×10^{10} vp (release titer)
- 1e) NI after 1-dose of Ad26.COV2.S 1.25×10^{10} vp versus 1-dose of Ad26.COV2.S 5×10^{10} vp (release titer)

In this set, NI will be demonstrated in terms of humoral immune response expressed by the GMCs of S-ELISA, 28 days post-dose 1, using a NI margin of 2/3 for the GMC ratio (GMC [9×10^{10} vp, 2.5×10^{10} , 7×10^{10} vp, 3.5×10^{10} vp, or 1.25×10^{10} vp]/GMC 5×10^{10} vp).

Post-dose 2

- 2a1) NI after 2-doses of Ad26.COV2.S 9×10^{10} vp versus 1-dose of Ad26.COV2.S 5×10^{10} vp (release titer)
- 2a2) NI after 2-doses of Ad26.COV2.S 9×10^{10} vp versus 2-doses of Ad26.COV2.S 5×10^{10} vp (release titer)
- 2b1) NI after 2-doses of Ad26.COV2.S 2.5×10^{10} vp versus 1-dose of Ad26.COV2.S 5×10^{10} vp (release titer)
- 2b2) NI after 2-doses of Ad26.COV2.S 2.5×10^{10} vp versus 2-doses of Ad26.COV2.S 5×10^{10} vp (release titer)
- 2c1) NI after 2-doses of Ad26.COV2.S 7×10^{10} vp versus 1-dose of Ad26.COV2.S 5×10^{10} vp (release titer)
- 2c2) NI after 2-doses of Ad26.COV2.S 7×10^{10} vp versus 2-doses of Ad26.COV2.S 5×10^{10} vp (release titer)
- 2d1) NI after 2-doses of Ad26.COV2.S 3.5×10^{10} vp versus 1-dose of Ad26.COV2.S 5×10^{10} vp (release titer)
- 2d2) NI after 2-doses of Ad26.COV2.S 3.5×10^{10} vp versus 2-doses of Ad26.COV2.S 5×10^{10} vp (release titer)

[figure not shown]
2e1) NI after 2-doses of Ad26.COV2.S 1.25×10^{10} vp versus 1-dose of Ad26.COV2.S 5×10^{10} vp (release titer)

2e2) NI after 2-doses of Ad26.COV2.S 1.25×10^{10} vp versus 2-doses of Ad26.COV2.S 5×10^{10} vp (release titer)

In this set, NI will be demonstrated in terms of humoral immune response expressed by the GMCs of S-ELISA, 14 days post-dose 2 (9×10^{10} vp, 2.5×10^{10} vp, 7×10^{10} vp, 3.5×10^{10} vp, or 1.25×10^{10} vp) and 28 days post-dose 1 or 14 days post-dose 2 (5×10^{10} vp), using a NI margin of 2/3 for the GMC ratio ($\text{GMC } 9 \times 10^{10} \text{ vp, } 2.5 \times 10^{10} \text{ vp, } 7 \times 10^{10} \text{ vp, } 3.5 \times 10^{10} \text{ vp, or } 1.25 \times 10^{10} \text{ vp}] / \text{GMC } 5 \times 10^{10} \text{ vp}$).

[Figure 2](#) depicts a tree-based schema for testing the 2 sets of non-inferiority hypotheses (1 dose and 2 doses) controlling the family-wise error rate at alpha = 0.025 (1-sided).

Figure 2: Decision Tree-Based Hypothesis Testing

9.2. Sample Size Determination

The number of participants chosen is to provide sufficient power for the non-inferiority comparisons stated in Section 9.1.

The following assumptions were made in the sample size determinations:

- Log transformed (log10 scale) immune response data are normally distributed
- A common standard deviation (SD): SD 0.5 (log10 scale) of the immune response log transformed data
- Non-inferiority margin $\log_{10}(2/3) = -0.176$

- Alpha 0.025 (one-sided). Using a Bonferroni correction, Type I error will be split equally over the 1-dose and 2-dose comparisons: 0.0125 (1-sided) for 1- and 2-dose NI comparisons
- Power 90%

Based on the above assumptions, assuming approximately a 10.2% dropout, a sample size of 225 participants per active vaccine group (see [Table 1](#)) is needed to detect non-inferiority of testing 1-dose and 2-doses of 9×10^{10} vp, 2.5×10^{10} vp, 7×10^{10} vp, 3.5×10^{10} vp, and 1.25×10^{10} vp Ad26.COV2.S as the test groups versus 1-dose and 2-doses of 5×10^{10} vp Ad26.COV2.S (release titer) as the reference groups, with 90% power.

A target of approximately 240 participants (40 seronegative and 20 seropositive participants) per dose regimen in Groups 1, 3, 5, and 6 will be enrolled to further characterize the innate, pro-inflammatory and other relevant (eg, pro-thrombotic) responses to Ad26.COV2.S to better understand a possible risk to TTS events. This target may not be met due to the challenges of enrolling seronegative subjects into the study, so sub-study enrollment may stop at lower numbers.

Participants in the main study and sub-study (participants who are seronegative at enrollment or baseline) may be combined for the analysis.

[Table 7](#) shows how the power will be affected with 10%, 20%, 30%, 40%, 50% and 60% dropout due to various reasons (eg, lost to follow-up, participants with major protocol deviations with impact on immunogenicity, participants who become N-seropositive during the study or with a confirmed SARS-CoV-2 infection, and participants who received their vaccination outside the allowed window).

Table 7: Power Based on % of Drop Out

Regimen	sample size at enrollment per arm	group	% drop out since enrollment					
			10%	20%	30%	40%	50%	60%
9×10^{10} vp (sample size of main study and sub-study)	252 (212+40)	1	92.00%	88.60%	83.70%	76.80%	68.10%	57.20%
2.5×10^{10} vp (sample size of main study and sub-study)	252 (212+40)	5	92.00%	88.60%	83.70%	76.80%	68.10%	57.20%
7×10^{10} vp (main study)	212	2	89.40%	85%	79.90%	72.70%	63.70%	53.00%
5×10^{10} vp (sample size of main study and sub-study)	252 (212+40)	3	92.00%	88.60%	83.70%	76.80%	68.10%	57.20%
3.5×10^{10} vp (main study)	212	4	89.40%	85.00%	79.90%	72.70%	63.70%	53.00%
1.25×10^{10} vp (sample size of main study and sub-study)	252 (212+40)	6	92.00%	88.60%	83.70%	76.80%	68.10%	57.20%

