9.4.2. Primary Endpoint(s)

Immunogenicity Endpoints

For each NI comparison between post-dose 1 ($[9 \times 10^{10}$ vp, 2.5×10^{10} , 7×10^{10} vp, 3.5×10^{10} vp, or 1.25×10^{10} vp] versus 5×10^{10} vp), estimated humoral immune response differences will be expressed as ratios of GMCs of S-ELISA (GMC [9×10^{10} vp, 2.5×10^{10} , 7×10^{10} vp, 3.5×10^{10} vp, or 1.25×10^{10} vp]/GMC 5×10^{10} vp), 28 days post-dose 1 with corresponding 97.5% confidence interval (CI) (2-sided) (Type 1 error 0.0125 for each comparison).

Similarly, for each NI comparison between post-dose 2 ($[9 \times 10^{10}$ vp, 2.5×10^{10} , 7×10^{10} vp, 3.5×10^{10} vp, or 1.25×10^{10} vp] versus 1- or 2-doses of 5×10^{10} vp), estimated humoral immune response differences will be expressed as ratios of GMCs of S-ELISA (GMC [9×10^{10} vp, 2.5×10^{10} , 7×10^{10} vp, 3.5×10^{10} vp, or 1.25×10^{10} vp]/GMC 5×10^{10} vp), 28 days post-dose 1 or 14 days post-dose 2 with corresponding 97.5% confidence interval (CI) (2-sided) (Type 1 error 0.0125 for each comparison).

In both sets (1 dose and 2 doses) of comparisons above, 97.5% CIs (2-sided) for mean difference in log₁₀-transformed S-ELISA titers between 2 groups will first be calculated and then back-transformed to the original scale to obtain the GMC ratios and the associated 97.5% CIs (2-sided). Non-inferiority between the groups will be established if the 97.5% CI of the estimated GMC ratio of the groups entirely lies above 2/3.

In the 1-dose (dose 1 of the 2-dose regimen) and 2-dose set NI comparisons, hierarchical testing after administration of a single-dose and 2 doses will be applied independently, as reflected in the Decision Tree-based Hypothesis Testing (Figure 2 and Section 9.1). The non-inferiority analyses will be done on the NI analysis set.

- Note: If a large number of participants become infected during the study (as assessed eg, by N-seroconversion or by PCR confirmation) or are SARS-CoV-2 seropositive at baseline, the main study and sub-study participants (seronegative at baseline) may be combined.
- If the power of the combined main study and sub-study is less than 80% then seropositive subjects at baseline will be included in the analysis. Further details of the analysis will be provided in the SAP.

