5.5.3.1. Non-Inferiority Analysis- Immune Response

Formal NI testing will be applied to demonstrate non-inferiority of immunogenicity. Non-inferiority will be analyzed by vaccine dose levels. As described in section 4, only one of the two scenarios will be considered for non-inferiority hypothesis testing at primary analysis. If there is an overall loss of $> 40\%$ evaluable data points in the NI set at Day 29 (defined as number of evaluable participants in the NI set at D29/total number of subjects in Table 4), the population in scenario 2 will be used for primary analysis.

- **Scenario 1 (base case scenario):** non-inferiority will be performed on the NI set including participants from the main and the sub study. A linear regression analysis with only one main effect (dose level) will be fitted, with log-transformed (\log_{10} scale) SARS-CoV-2 S-protein specific antibody concentration (S-ELISA) as the response variable and dose level as the independent variable.
- **Scenario 2:** Non-inferiority will be performed on the PPI set including participants from the main study and sub-study. A linear regression analysis with two main effects (dose level and SARS-CoV-2 serostatus at baseline) will be fitted, with log-transformed (\log_{10} scale) SARS-CoV-2 S-protein specific antibody concentration (S-ELISA) as the response variable and dose level and SARS-CoV-2 serostatus at baseline as the independent variables.

Participants with missing serostatus at baseline will not be included in this analysis.

Level of Significance

For each of the 1-dose and 2-dose vaccine regimens hypothesis, the type I error rate α will be set to 0.0125 (1-sided) and non-inferiority (NI) tests will be confirmed by constructing the corresponding 97.5% confidence interval (2-sided) which is equivalent to using $\alpha = 0.025$ (1-sided) with 98.75 (1-sided CI).

Multiplicity Adjustment

The family-wise error rate (FWER) at $\alpha = 0.025$ (one-sided), will be controlled by:

Splitting the Type I error rate $\alpha = 0.025$ into two (i.e., $\alpha = 0.0125$) using Bonferroni correction for the independently tested 1 and 2 doses NI hypotheses (see

[Figure 1](#)).

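### The 1-dose and 2-dose families are each held at one-sided 0.0125 with no transfer of alpha in the text; letting a fully rejected family pass its share on would add some power within the planned 0.025

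*Protocol*

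**What the plan says.** Protocol 9.1 defines five post-dose 1 hypotheses and ten post-dose 2 hypotheses and says: "The following 2 sets of hypotheses (1 dose and 2 doses) will independently be tested sequentially". Protocol 9.2 halves the one-sided 0.025 between the two families: "Using a Bonferroni correction, Type I error will be split equally over the 1-dose and 2-dose comparisons". Protocol 9.4.2 repeats that "hierarchical testing after administration of a single-dose and 2 doses will be applied independently" and gives one decision rule for every test: "Non-inferiority between the groups will be established if the 97.5% CI of the estimated GMC ratio of the groups entirely lies above 2/3".

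SAP 5.5.3.1 describes the same control of the overall error, "using Bonferroni correction for the independently tested 1 and 2 doses NI hypotheses", and sets alpha to 0.0125 in its interval formula. No sentence in either document moves alpha from one family to the other. The decision trees (Protocol Figure 2, SAP Figure 1) could not be read in the text available. However, a transfer shown there would conflict with the single interval level in the text around them.

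**The concern.** When every hypothesis in one family has been rejected, that family's 0.0125 has no further use under this plan. The other family is still tested at 0.0125, although the plan's overall limit is 0.025. A standard gatekeeping or graphical procedure would hand the unused 0.0125 over.

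This matters here because power is what the late changes were meant to protect. Amendment 7 reordered the hypotheses, and SAP version 2 pooled the main study and sub study, both because infections were removing evaluable participants. A transfer rule needs no further participants and changes neither the order of testing nor the analysis population. It helps most at the end of each sequence, where power is lowest.

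**Working it through.** **Inputs from the documents.** One-sided alpha 0.0125 per family; margin 2/3, so δ = −log10(2/3) = 0.1761; SD 0.5 on log10; 90% power; 10.2% dropout; 225 per group (Protocol 9.2). Group sizes with the sub study are 265 or 225 (SAP Table 4) and 252 or 212 (Protocol Table 7). Blinded N-serology positivity was 27% at Day 29 and 38% at Day 71 (SAP section 3).

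**Assumed, not in the documents.** All true ratios 1 unless stated; total loss 30% at Day 29 and 40% at Day 71; within-participant correlation 0.6; dose 2 raises the log10 response by 0.3.

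**1. The plan's own figure.** n = 2σ²(z0.9875 + z0.90)²/δ² = 2 × 0.25 × (2.241 + 1.282)² / 0.1761² ≈ 200.1, so 201 evaluable per group. Then 201/(1 − 0.102) = 224, against 225 stated. The sample size reproduces.

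**2. Ceiling for one comparison.** Power = Φ(δ/(σ√(2/n)) − z).
- At n = 202 (225 less 10.2%): 90.3% at 0.0125 and 94.3% at 0.025, a difference of 4.0 points.
- At n = 159 (265 less 40%): 81.6% and 88.1%, a difference of 6.5 points. SAP Table 4 prints 81%.
- At 60% loss with Table 7 sizes, the difference reaches 10 to 11 points.

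These figures assume 0.025 is always available. Recycling returns only part of them, because alpha moves only after all five 1-dose tests, or all ten 2-dose tests, have passed.

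**3. Error rate with recycling.**
- If only one family contains true null hypotheses, its first true null is tested at 0.025 at most.
- If both do, alpha can move only after one family is fully rejected, which already requires a false rejection at 0.0125. The total is at most 0.0125 + 0.0125 = 0.025, whatever the correlation.
- Simulation (1,000,000 runs per case, correlation 0, 0.5 and 0.8) gave 0.0249 to 0.0253 when one family or its last 2-dose v 2-dose hypothesis was null and the rest clearly non-inferior. The plain split gave about 0.0125 in the same cases.

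**4. No claim is lost.** A test that passes at 0.0125 also passes at 0.025, and the order is unchanged. Simulation found no lost claim in any scenario.

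**5. Power gained, all true ratios 1, SAP Table 4 sizes (200,000 runs), 2-dose v 2-dose claims in test order.**

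| Dose (×10^10 vp) | Plain split | With transfer | Gain (points) |
|---|---|---|---|
| 9 | 81.5% | 84.6% | 3.1 |
| 2.5 | 70.7% | 75.5% | 4.8 |
| 7 | 61.2% | 67.5% | 6.3 |
| 3.5 | 54.3% | 61.6% | 7.3 |
| 1.25 | 50.5% | 58.3% | 7.8 |

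The 1-dose claims gain 1.5 to 4.7 points. The chance of making all 15 claims rises from about 39% to 52%. With Protocol Table 7 sizes the 2-dose v 2-dose gains are 3.1 to 7.6 points.

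**6. Sensitivity.**
- Loss of 27% and 38%, correlation 0 to 0.8, either table's sizes: the last 2-dose test gains 7.8 to 8.4 points; the 1-dose tests gain 0.8 to 6.0.
- True ratios 0.95, 0.90 and 0.85 for 3.5, 2.5 and 1.25×10^10 vp: the 2-dose v 2-dose claims gain about 1 point (9×10^10 vp), 3 to 4 (2.5, 7 and 3.5×10^10 vp) and 4 (1.25×10^10 vp); the 1-dose claims gain 0.5 to 3.
- True ratio 0.76 at 1.25×10^10 vp only: gains of about 0 to 1 point, at most about 1.5 on the last test.

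**The case against.** The strongest reply is that nothing is wrong. The Bonferroni split controls the family-wise error as stated, and a plan may leave alpha unused. That stands: this is a missed efficiency, and a reader who infers a flaw in error control goes beyond the documents.

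Second, Protocol 2.1 ties the 1-dose and 2-dose regimens to separate efficacy studies, so the sponsor may want each family's conclusion to stand alone. This carries limited weight. Recycling never withdraws a claim made at 0.0125, and Amendment 6 put post-dose 1 and post-dose 2 data into a single primary analysis. It would matter if a 1-dose result were issued at one of the further interim analyses that Protocol 9.5 allows and were later retested at another interval level.

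Third, a reader might infer that the plan gives away 8 points in general, or 10 to 11. Neither follows. About 8 points belongs only to the last 2-dose test with every true ratio equal to 1. The 10 to 11 is the single-comparison ceiling at 60% loss. The lower doses are in the trial to mimic degradation, so a decline with dose is plausible, and the gain then shrinks sharply.

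Fourth, the transfer has a cost in actual error, which can rise from about 0.0125 to 0.025 when one family is wholly non-inferior. That is correct, although 0.025 is the limit the plan sets itself.

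**Conclusion.** The visible text leaves 0.0125 unused whenever one family succeeds in full. A transfer rule would be more powerful at the same 0.025 limit, with no claim put at risk. When all doses are truly equivalent and losses are close to those seen in the blinded data, the gain is about 3 to 8 points for the 2-dose v 2-dose claims and about 1 to 5 points for the 1-dose claims. With a modest dose decline it is about 0.5 to 4 points, and it nearly vanishes if the lowest dose is clearly weaker.

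The error-rate and no-lost-claim results are general. The sizes rest on the assumed true ratios, loss rates, correlation and dose-2 rise. The 27% and 38% are N-serology positivity, not total loss. The statement that no alpha is passed on is limited to the text, since the decision-tree figures were not visible. The point is minor and optional.

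**What to change.** Before unblinding, state in Protocol 9.1, 9.2 and 9.4.2 and in SAP 5.5.3.1: if all hypotheses in one family are rejected at one-sided 0.0125, the other family is tested in the same order at one-sided 0.025, using 95% two-sided confidence intervals.

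One added sentence is not enough, because the existing text would contradict it. The following must change as well:
- the rule in Protocol 9.4.2 that every comparison uses a 97.5% interval;
- the Level of Significance and Multiplicity Adjustment text in SAP 5.5.3.1;
- the alpha in the SAP interval formula. The formula uses the 1 − α/2 quantile, so its α should be the two-sided value for the interval in use (0.025 for 97.5%, 0.05 for 95%), where it now reads 0.0125;
- Protocol Figure 2 and SAP Figure 1.

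The cost is these edits, a second interval level in the report when the transfer applies, and use of the full 0.025 in cases where the plain split would use about half. If the sponsor prefers the plain split so that each regimen's result stands alone, one sentence saying so would settle the matter. If unblinding has already taken place, the rule should not be added.

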3. SAMPLE SIZE DETERMINATION

The number of participants chosen is to provide sufficient power for the non-inferiority comparisons.

The following assumptions were made in the sample size determinations:

Log transformed (\log_{10} scale) immune response data are normally distributed

A common standard deviation (SD): SD=0.5 (\log_{10} scale) of the immune response log transformed data

Non-inferiority margin = $\log_{10}(2/3) = -0.176$

Alpha = 0.0125 (1-sided) for 1- and 2-dose NI comparisons

- Alpha = 0.025 (one-sided). Using a Bonferroni correction, Type I error will be split equally over the 1-dose and 2-dose comparisons: 0.0125 (1-sided) for 1- and 2-dose NI comparisons

Power = 90%

Based on the above assumptions, and approximately a 10% dropout, a sample size of 225 participants per active vaccine group (see [Table 2](#)) is needed to detect non-inferiority of testing 1-dose and 2-doses of 9×10^{10} vp, 2.5×10^{10} vp, 7×10^{10} vp, 3.5×10^{10} vp, and 1.25×10^{10} vp Ad26.COV2.S as the test groups versus 1-dose and 2-doses of 5×10^{10} vp Ad26.COV2.S (release titer) as the reference groups, with 90% power (main study sample size assessment).

The originally intended NI population was comprised of participants from the main study who were SARS-CoV-2 seronegative at baseline and non-previously vaccinated. In addition, participants becoming infected with SARS-CoV-2 during the study are excluded from this population from the time of infection.

Participants were screened using a local SARS-CoV-2 serology test to ensure only participants who were seronegative at baseline were enrolled in the main study. However, a preliminary blinded evaluation of central N-serology results in main study participants at Day 29 and Day 71 showed that overall, 27% and 38% of participants, respectively, were N-serology positive at these time points. The higher-than-expected N-serology positive status at Day 29 and Day 71 indicated that participants became infected during the study and/or local serology tests were not sufficiently sensitive, affecting the power of the study.

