For the sub-study (initiated to further characterize the innate, pro-inflammatory and other relevant (e.g., prothrombotic) responses to Ad26.COV2.S to better understand a possible risk to TTS events), a target of approximately 240 participants will be enrolled and will receive a 2-dose vaccination regimen at either 9×10^{10} vp, 2.5×10^{10} vp, 5×10^{10} vp, or 1.25×10^{10} vp. As participants in the sub-study share common blood sampling timepoints with the main study, data from both cohorts can be merged for analyses. Due to the higher-than-expected N serology positive results in the main study affecting the power of the study, the non-inferiority assessment will combine participants from the main study and sub-study.

Table 4 below shows how, when combining main and sub study participants (randomized as SARS-CoV-2 seronegative at baseline based on local serology by finger prick testing), the power is affected due to a hypothetical 10%, 20%, 30%, 40%, 50% and 60% loss of evaluable participants (lost due to various reasons, e.g. lost to follow-up, participants with major protocol deviations with impact on immunogenicity, participants who become infected with SARS-CoV-2, participants who received their vaccination outside the allowed window, etc.).

Table 4: Impact of loss of evaluable subjects on NI assessment power

Dose level	Sample size at enrollment per arm (main study + sub study)	Group	% loss of evaluable participants since enrollment					
			10%	20%	30%	40%	50%	60%
9x1010 vp	265(225+40)	1	94%	91%	87%	81%	73%	62%
2.5x1010 vp	265(225+40)	5	94%	91%	87%	81%	73%	62%
7x1010 vp	225 (225+0)	2	90%	86	81%	74%	65%	54%
5x1010 vp	265(225+40)	3	94%	91%	87%	81%	73%	62%
3.5x1010 vp	225 (225+0)	4	90%	86	81%	74%	65%	54%
1.25x1010 vp	265(225+40)	6	94%	91%	87%	81%	73%	62%

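### The 90% power and the per-dose power tables describe each comparison tested alone, but NI is tested in a gated sequence, so every dose after the first has a lower chance of being declared non-inferior than the plan states

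*Protocol*

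**What the plan says.** Protocol 9.2 says the sample size should give enough power for the NI comparisons listed in Section 9.1. It names one and two doses of all five test levels, compared with "release titer) as the reference groups, with 90% power". SAP 3 repeats the claim: "release titer) as the reference groups, with 90% power (main study sample size assessment". Protocol Table 7 and SAP Table 4 ("Impact of loss of evaluable subjects on NI assessment power") then give one power for each dose group at 10% to 60% loss.

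The testing rule is in Protocol 9.1: "The following 2 sets of hypotheses (1 dose and 2 doses) will independently be tested sequentially". The post-dose 1 list runs 9, 2.5, 7, 3.5, 1.25×10^10 vp (1a to 1e). The post-dose 2 list takes the doses in the same order, with two tests per dose (2a1 to 2e2). Protocol 2.1 puts conditions between steps, and Protocol 9.4.2 calls the testing hierarchical within each set. SAP 2 and 5.5.3 repeat the lists. Alpha is split once, between the two families: "0.0125 (1-sided) for 1- and 2-dose NI comparisons". It is not split within a family.

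Protocol 9.4.2 also has a rule that depends on power. If the combined main study and sub-study have less than 80% power, participants seropositive at baseline enter the NI analysis.

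**The concern.** Because alpha is not divided within a family, error control relies on the gate: a dose cannot be declared non-inferior unless all doses before it have passed. The chance of declaring NI for a later dose is therefore the chance of passing its own test and every earlier one. Neither document gives that figure.

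The ranking in the tables shows the gap. SAP Table 4 gives 1.25×10^10 vp 81% at 40% loss, and gives 7 and 3.5×10^10 vp 74%. Yet 1.25 is tested last and needs both of those to pass, so its chance of success cannot exceed theirs.

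Two things are at stake. The lower doses are meant to inform product expiry, and 3.5 and 1.25×10^10 vp are at steps four and five (2.5 is second). The 80% rule can also select a different primary population depending on which power is meant.

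**Working it through.** **Inputs**
- SD: "A common standard deviation (SD): SD 0.5 (log10 scale) of the immune response log transformed data" (Protocol 9.2).
- Margin: "using a NI margin of 2/3 for the GMC ratios" (Protocol 9.1), so δ = −log10(2/3) = 0.1761.
- One-sided alpha 0.0125, so the critical value is c = 2.2414.
- Dropout 10.2% and 225 per group (Protocol 9.2).
- True GMC ratio: absent from the list that begins "The following assumptions were made in the sample size determinations". Taken as 1 for every dose, because that value returns the plan's own size.

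**Reproducing the plan**
- n per arm = 2 × 0.5² × (2.2414 + 1.2816)² / 0.1761² = 200.1, so 201, or 202 with the t distribution. Then 202 / 0.898 = 224.9, so 225.
- One comparison at 202 v 202: SE = 0.5 × √(2/202) = 0.0498, and Φ(0.1761/0.0498 − 2.2414) = Φ(1.298) = 90.3%. With t it is 90.1%.
- SAP Table 4 at 40% loss: 265 × 0.6 = 159 per arm gives 81.2% (stated 81%); 225 × 0.6 = 135 per arm gives 73.8% (stated 74%).

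The stated figures are therefore two-arm powers for a single test. Table 4's 225 rows also assume equal arms. Against the larger reference arm (135 v 159), the single-test power is 77.5%.

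**Adding the gate**

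Write the reference mean as σz/√n₀, with z standard normal. Given z, the tests are independent, and test j passes with probability

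pⱼ(z) = Φ( [δ − c·σ·√(1/nⱼ + 1/n₀) − σz/√n₀] / [σ/√nⱼ] ).

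The chance of passing the first k tests is the integral of φ(z) × p₁(z) × … × p_k(z). The table uses simulated pooled-variance t intervals; the integral agrees to within about one percentage point.

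| Post-dose 1, order 9 / 2.5 / 7 / 3.5 / 1.25 | In sequence | Stated |
|---|---|---|
| 202 per arm | 90/83/78/74/71% | 90% each |
| SAP Table 4, 30% loss | 87/79/71/65/61% | 87/87/81/81/87% |
| SAP Table 4, 40% loss (159 or 135) | 81/70/61/54/50% | 81/81/74/74/81% |
| Protocol Table 7 (252 or 212), 40% loss | 79/67/57/50/46% | 76.8/76.8/72.7/72.7/76.8% |

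At 10% loss the last dose has about 76% at Table 7 sizes (stated 92%) and about 79% at Table 4 sizes (stated 94%).

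The shared reference group matters. Multiplying as if the tests were independent gives 0.90^5 = 59%, which is too low.

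Table 7 does not fully reproduce even as single-test power: its 252 row at 40% loss states 76.8%, and the formula gives 79.0%. The comparison above does not depend on this.

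**Sensitivity to the assumed ratios** (last dose; 202 per arm, then Table 4 at 40% loss)
- 9 and 7×10^10 vp each 0.1 log10 above the reference: 78%, 61%.
- All ratios 1: 71%, 50%.
- log10 GMC rising by 0.1 per log10 of dose: 44%, 29%. Tested alone, the last dose would then have 53% and 43%, so part of the fall comes from the lower response and not from the gate.

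**Post-dose 2 family (ten tests)**
- If the second dose raises the GMC by 0.1 log10 or more, the comparisons with one dose are nearly certain to pass, and the last step is again about 71% and 50%.
- With no rise, it is 55–64% at 202 per arm and 31–42% at 40% loss, for an assumed within-person correlation of 0 to 0.8.

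**The 80% rule**

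Read as single-comparison power, Table 7's 252 rows stay above 80% through 30% loss (83.7%) and fall below it at 40% (76.8%). Read as the power to declare the last dose, it is already below 80% at 10% loss. The two readings would select different populations between those points.

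**The case against.** The strongest reply is that nothing has been miscalculated. The 225 and 90% reproduce, SAP Table 4 reproduces, and power for the comparisons can fairly be read as power per comparison. The documents do not claim 90% for a whole sequence. That stands as far as it goes. But Protocol 9.2 refers to the comparisons in Section 9.1, which are the sequence, and names all five doses at 90% without saying that the figure is for one isolated test.

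The plan does not overlook order entirely. Protocol 9.1 moves 2.5 ahead of 7×10^10 vp because the smaller group is more likely to fail. The effect is recognised but not quantified.

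The exact gating is partly out of sight. The decision-tree figure is not shown, Protocol 2.1 has no condition between 2.5 and 7, and the letter key in SAP 5.5.3.1 lists 3.5 before 7. The ordered lists in Protocol 9.1 and SAP 2 support a strict sequence. Swapping 7 and 3.5, which have equal sizes, would leave the numbers at each step unchanged when all ratios are 1.

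A reader might infer two stronger things that the documents do not support:
- That these power figures set the SAP's 40% loss threshold. SAP 4.2 cites Table 4 only for the total number of subjects, as a denominator.
- That they led to a wrong test order. The order was changed because of relative group size, for which single-comparison power is a reasonable input.

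**Conclusion.** Wrong as written; should be fixed. For every dose after the first, the stated power is not the chance that the design declares NI. With all true ratios at 1, the shortfall for the last dose is about 19 percentage points at the planned size (90% stated, 71% in sequence) and about 31 at 40% loss in SAP Table 4 (81% stated, 50% in sequence).

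These sizes rest on the unstated ratio of 1, SD 0.5, the shared reference group and a strict gate. They should not be read as the real chance of success: the last-dose figure is lower if low doses respond less and somewhat higher if the high doses respond more. What does not depend on the ratios is that a later dose cannot have a higher chance of being declared than a dose that gates it.

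A reader might also infer that error control fails or that the trial must be enlarged. Neither follows. The fixed sequence with the alpha split controls type I error as planned, and the point concerns only how power is stated.

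**What to change.** - In Protocol 9.2, SAP 3, Protocol Table 7 and SAP Table 4, label the 90% and the table entries as power for a single comparison tested alone.
- Add sequence-adjusted rows to both tables, computed separately at each table's own sizes (252/212 and 265/225) and for all six loss columns. Figures from one table should not be carried into the other.
- Give separate rows for the post-dose 1 family (five tests) and the post-dose 2 family (ten tests). For the second, state the assumed rise after dose 2 and the within-person correlation.
- State the assumed true GMC ratios and show a range, including lower responses at the low doses.
- In Protocol 9.4.2, say which power the 80% rule uses and for which dose, and reconcile that rule with the 40% loss rule in SAP 4.2.

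The cost is a few sentences and a recomputed table. The stated figures become less favourable. Sample size, alpha, test order and analysis method do not change.
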